4.1. Study 1. Evaluating the Diagnostic Accuracy of CoCoA-PAD subtests

Participants

A total of 120 participants will be recruited: 60 participants with subjective cognitive decline (SCD) and 60 participants with mild cognitive impairment (MCI). Participants will be classified post-recruitment into four distinct diagnostic groups: healthy controls, preclinical AD, prodromal AD, and non-AD related MCI. Figure 3 provides a flow of the estimated frequencies of each diagnostic group within the sample.

Sampling

This study will use a stratified sampling approach with post-hoc diagnostic classification. A prospective quasi-experimental between-group research design will be employed.

A stratified sampling approach will ensure that key demographic information, including years of education and ethnicity, will match national population demographics of the UK. 2021 census data revealed that 6% of 70–74-year-olds in the UK are from non-white ethnic minority backgrounds. However, given that people from minority ethnic backgrounds are significantly more likely to have dementia but less likely to receive a diagnosis (Okeoghene Ighomereho, 2025), for the purpose of this study, the stratified sampling target will be inflated to 10%.

Similarly, 2021 census data has mapped the educational attainment of the UK population. No age-specific education attainment values were published, but regional values have been published, and Plymouth demographics have been selected for this study. This is based on coastal communities having higher rates of dementia, lower rates of diagnosis, and significant social inequalities which often exclude them from research (Alzheimer’s Research UK, 2024). This study will replicate educational attainment values, with provision for 5% variation in the recruitment to each education level – see Table 1.

Table 1. Educational Attainment and Stratified Sampling Target

Educational Attainment	Plymouth Demographics	CoCoA-PAD Recruitment Target Range
No Qualification	17%	14-26
Level 1 (O level any grade)	10%	6-18
Level 2 (O levels passes)	14%	11-23
Apprenticeship	6%	1-13
Level 3 (A level equivalent)	17%	14-26
Level 4 (3 rd level qualifications)	34%	35-47
Other	2%	0-8

Procedure

Participants will be recruited and classified post-recruitment into diagnostic groups on the basis of AD biomarker results (pTau-217) and performance on the M-ACE, using a cut-off score of 20 for MCI (Potts et al., 2022).

Measures

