For this study, we will use the ALZpath pTau217 Simoa® immunoassay (the platform used by the UK DRI Dementia Biomarker Factory), which has been validated in a large, international JAMA Neurology study and supports a two-cutoff, three-range workflow (Ashton et al., 2024). In this study, which included a large sample (n = 786) spanning memory-clinic populations, ALZpath p-tau217 showed diagnostic accuracy comparable to CSF measures for detecting abnormal A β and tau. To reduce false classifications and limit confirmatory testing, the authors recommend two plasma p-tau217 thresholds:

1. < 0.40 pg/mL to rule-out amyloid pathology
2. > 0.63 pg/mL to rule-in amyloid pathology
3. 0.40–0.63 pg/mL “grey zone” – confirmatory testing required.

This approach was reproducible across cohorts and substantially reduced the need for confirmatory testing while maintaining high overall accuracy (Ashton et al., 2024). This approach will be used for the purposes of the current study.

Patient Health Questionnaire (PHQ-2) and Generalised Anxiety Disorder (GAD-2)

The PHQ-2 is a brief screening measure for clinical depression. It consists of only 2 items, both of which related to the core diagnostic criteria for clinical depression outlined in the DSM-V. Meta-analytic research has identified that a cut off score of ≥ 3 has good diagnostic accuracy for identifying clinical depression (AUC = 0.88) (Aktürk et al., 2025).

The GAD-2 is a brief screening measure for generalised anxiety. It consists of only 2 items, both of which related to the core diagnostic criteria for generalised anxiety outlined in the DSM-V. Meta-analytic research has identified that a cut off score of ≥ 3 has good diagnostic accuracy for identifying generalised anxiety (AUC = 0.828) (Mitchell et al., 2016).

Insomnia Severity Index (ISI)

The ISI is a brief self-report questionnaire that assesses sleep quality and disturbances over the past month. It includes 7 items and takes less than 5 minutes to administer. The ISI has been validated in a large older adult cohort, and achieved adequate reliability and validity (Dragioti et al., 2017). Higher scores on the ISI indicates greater insomnia severity. The total score is divided into four categories: no clinically significant insomnia (ISI = 0–7); sub-threshold insomnia, (ISI = 8–14); moderate clinical insomnia (ISI = 15–21); and severe clinical insomnia (ISI = 22–28).

Numeric Rating Scale (NRS) for pain

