Although blood tests are common medical procedures, they can cause psychological distress for some participants. Common reactions include anxiety, nervousness, or anticipatory stress, particularly among individuals with needle phobia (trypanophobia) or a history of negative medical experiences. Some participants may feel faint, dizzy, or panicked before or during the procedure.

To minimise psychological distress, all blood tests will be conducted by trained clinical research staff, such as NHS phlebotomists or nurses, who are experienced in working with older adults. Participants will receive clear, simple explanations of the procedure in advance, including reassurance that the test is safe and quick, and optional. They will have the opportunity to ask questions. During the blood draw, participants will be encouraged to sit or lie in a comfortable position, and will be monitored for signs of distress, dizziness, or fainting. If needed, breaks and recovery time will be provided. Researchers will take a calm and supportive approach throughout and ensure that the environment is as relaxed and non-threatening as possible.

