- Include sample manifest with participant IDs and aliquot details

8. Plasma Analysis and Sharing

- The samples will be received by the UCL Biomarker Factory, who will complete the biomarker analysis using Quanterix Simoa® ALZpath pTau 217.
- A research database with pTau217 levels and the participant ID will be created and shared with the CI via the share function on MS SharePoint, which will include multi-factor log-in procedures, access control and an expiration.

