Raw anonymised MRI data is archived in original DICOM format on the DICOM server (AET: ORTHANC-Lin2) located on the University premises and connected to the University network. The MRI raw data is stored securely for at least 10 years. The BRIC Data Management Policy v1 (26/03/2021) provides a more detailed description of the BRIC procedures for data storage, retention and archiving).

Raw Blood Samples

Plasma samples will be sent to UCL's Biomarker Factory for analysis. The Biomarker Factory will analyse the plasma samples, and produce an anonymised dataset, which will include the participants' ID codes and pTau217 results. The plasma samples will not be used for any additional research and will be destroyed using bleach once the analysis has been completed and verified.

The UCL Biomarker Factory retain an encrypted version of the anonymous database on a locked Biomarker Factory channel on MS Teams for a period of at least ten years. This database will be transferred securely using MS Teams to the CoCoA-PAD CI, who will transfer the results into the REDCap database, and store this database in an access-controlled folder on the CoCoA-PAD site file for a period of at least 10 years.

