11.3. Sample Size

Given that there are three independent studies, a justification of the proposed sample is outlined for each study.

Study 1: Diagnostic Accuracy of CoCoA-PAD Subtests

The aim of this study is to test whether CoCoA-PAD subtests can distinguish between healthy controls (i.e., people with subjective memory problems without any evidence of AD biomarkers or cognitive decline) and people with preclinical and prodromal Alzheimer's disease. This study uses a prospective research design, and therefore exact participant numbers in each diagnostic criteria cannot be determined until after data collection. Figure 3 provides an estimate of the final sample composition, which includes of 36 healthy controls, 18 people with preclinical AD, and 40 people with prodromal AD. A power calculation using a fixed one-way ANOVA (estimated effect size $f = 0.33$ (moderate effect), $k = 3$) required a minimum sample of 90 to achieve the required power ($\alpha = 0.05$, $1-\beta = 0.8$). Based on current projections (36 controls, 18 preclinical AD, and 40 with prodromal AD), this would be achieved.

Study 2: The relationship between CoCoA-PAD subtests and the health of key brain regions

This study aimed to measure the strength of the association between key brain regions and performance on CoCoA-PAD subtests. It includes a subgroup of study 1 participants. A power calculation using a linear multiple regression (fixed model, single regression coefficient, effect size f^2 (0.1, small) required a minimum sample of 64 participants to achieve the required power ($\alpha = 0.05$, $1-\beta = 0.8$).

Study 3: Testing whether CoCoA-PAD is sensitive to pathological cognitive decline in AD

This study aimed to compare 1 year change score (time 2 score – time 1 score) on CoCoA-PAD subtest scores in people with early Alzheimer’s disease and healthy controls. It includes a subgroup of study 1 participants. A power calculation using a matched pairs *t* test (Cohen’s *d* = 0.5 (moderate)) required a sample of 27 to achieve the required power ($\alpha = 0.05$, $1-\beta = 0.8$).

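### The pTau-217 grey-zone rule cannot be carried out because the study has no confirmatory test and no indeterminate group, and Study 1 has only 4 projected participants to spare over its stated 90

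*Protocol*

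**What the plan says.** Section 6.2 (pTau-217) lists a rule-out threshold of 0.40 pg/mL, a rule-in threshold of 0.63 pg/mL, and between them "0.40–0.63 pg/mL “grey zone” – confirmatory testing required". It adopts the scheme without reservation: "This approach will be used for the purposes of the current study".

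Section 4.1 classifies "on the basis of AD biomarker results (pTau-217) and performance on the M-ACE, using a cut-off score of 20 for MCI", and the outcome is closed: "Participants will be classified post-recruitment into four distinct diagnostic groups: healthy controls, preclinical AD, prodromal AD, and non-AD related MCI".

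Section 9.3 names a single assay at the receiving laboratory, "who will complete the biomarker analysis using Quanterix Simoa® ALZpath pTau 217". Section 9.4 then states: "The plasma samples will not be used for any additional research and will be destroyed using bleach once the analysis has been completed and verified".

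Section 7.5 describes the blood test to participants as optional ("including reassurance that the test is safe and quick, and optional").

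Section 11.3 sets a minimum of 90 for Study 1 and concludes: "Based on current projections (36 controls, 18 preclinical AD, and 40 with prodromal AD), this would be achieved".

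**The concern.** Each of the four groups needs a biomarker-positive or biomarker-negative status. Above the M-ACE cut-off, positive means preclinical AD and negative means healthy control. Below it, positive means prodromal AD and negative means non-AD MCI. A value between 0.40 and 0.63 pg/mL supplies neither status, and the protocol's route to resolving it is a test that the study does not contain. A participant who declines blood has no status either.

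Group membership defines the contrasts in primary objectives i and ii and the selection of participants for Study 3. With no rule written down, these participants could be dropped, called positive or called negative. Each choice gives different group sizes and different AUCs. Dropping them also changes what the AUC describes, because only clear-cut biomarker cases remain.

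**Working it through.** **1. Is there a confirmatory test anywhere?**
- Visit flow (Section 6.6): one blood test, no CSF or PET.
- Plasma procedure (Section 9.3): one assay, ALZpath pTau-217.
- Follow-up (Section 6.8): no blood test.
- Stored plasma (Sections 6.10 and 9.4): destroyed after analysis, no further use.
- MRI (Sections 4.2 and 5.1): structural and diffusion imaging, offered only at the Plymouth site, used as an outcome and not as a classifier.

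There is none, and Section 4.1 has no group for an unresolved result.

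**2. Reproducing the stated sample size.** Inputs from Section 11.3: one-way ANOVA, k = 3, f = 0.33, alpha 0.05, power 0.80. Power comes from the noncentral F distribution with df = 2 and N − 3, and noncentrality λ = N × f².
- N = 90: λ = 90 × 0.1089 = 9.80, power 0.793.
- N = 94: λ = 94 × 0.1089 = 10.24, power 0.811.
- Smallest N with power of at least 0.80: 92 (93 with equal groups).

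The stated 90 is reproduced to within 2 participants.

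**3. Margin.** 36 + 18 + 40 = 94, and 94 − 90 = 4. As a share, 4/94 = 4.3%, so a fifth unallowed loss takes Study 1 below 90.

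**4. Could the projection already allow for losses?** Of 120 recruits, 120 − 94 = 26 are outside the three groups. If the recruitment label and the final M-ACE status agree, 60 − (36 + 18) = 6 of these come from the SCD arm and 60 − 40 = 20 from the MCI arm. The 20 must also hold the non-AD MCI group. The text assigns none of the 26 to the grey zone or to missing blood. Figure 3 might, but it is not shown.

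**5. Effect of an unallowed loss.** The rate g is an assumption, applied equally to each group: N = 94 × (1 − g), preclinical n = 18 × (1 − g). Power is at N rounded to a whole number.

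| g | N | Power | Preclinical n |
|---|---|---|---|
| 0 | 94 | 0.811 | 18 |
| 10% | 85 | 0.767 | 16.2 |
| 20% | 75 | 0.708 | 14.4 |
| 30% | 66 | 0.645 | 12.6 |

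**6. AUC precision.** This uses the Hanley–McNeil standard error at an assumed AUC of 0.75. The 95% half-width for preclinical AD against controls goes from 0.147 with no loss to 0.155, 0.165 and 0.176 at 10, 20 and 30%. For prodromal AD against controls it goes from 0.109 to 0.115, 0.122 and 0.131.

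**7. Direction of the AUC shift, illustrative only.** In a bivariate-normal simulation, the top third on the biomarker are positive and a 20% band around the cut is removed. For assumed subtest–biomarker correlations of 0.3, 0.4 and 0.5, the AUC moves from 0.64 to 0.67, 0.69 to 0.73 and 0.74 to 0.78. The protocol gives neither the correlation nor the band. The model does not represent prodromal AD against controls, because those groups also differ on the M-ACE.

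**The case against.** The strongest reply is that handling of indeterminate results is ordinary SAP content and the SAP is not at hand. Section 11.4 promises a statistician-agreed plan, published before data collection. Section 4.6 has Study 1 and 2 data collected blind to biomarker status, with plasma sent for assay only afterwards. This stands in part: it weakens the worry that grey-zone participants would be assigned in the light of CoCoA-PAD scores. It does not remove the contradiction, because a SAP can add an analysis rule but cannot supply the test that Section 6.2 requires.

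A second reply is that the optional wording is reassurance about needles, that Section 6.6 lists blood in the standard flow, and that missing data have their own section (11.1). This also stands in part. The wording predicts no number of refusals, and it matters here only as a second route to a participant with no reference standard.

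Several stronger readings are tempting, and the documents do not support them:
- A reader might infer that 36/18/40 fail. The grey-zone rate is not stated, and some of the 26 other recruits may already be an allowance for it.
- A reader might infer that projected AUCs fail. The protocol projects none for CoCoA-PAD; the AUCs in Appendix 1 belong to reference tests.
- A reader might infer that Study 2 depends on group membership. It samples by location and is analysed by correlation and regression, with no group term stated.
- A reader might infer that Study 3 runs out of participants. It needs 18 from each of 36 and 40, so about half of each group would have to be lost first.

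**Conclusion.** The contradiction is certain from the text: Section 6.2 adopts a rule that Sections 4.1, 6.6, 6.8, 9.3 and 9.4 make impossible to follow. The reference standard for primary objectives i and ii is therefore undefined for results of 0.40–0.63 pg/mL.

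The effect on size is conditional. The margin is 4 participants over the stated 90. If 36/18/40 contain no allowance, a loss above about 4% breaches it, and assumed losses of 10, 20 and 30% bring power to about 0.77, 0.71 and 0.65. Those figures rest on the protocol's f = 0.33 and on equal proportional loss across the groups. AUCs from clear-cut cases alone would be less precise and may be optimistic, but by how much cannot be derived from the documents.

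**What to change.** Reconcile Sections 6.2, 4.1 and 11.3 before the biomarker results are linked to CoCoA-PAD scores.

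1. Replace confirmatory testing as a study rule with a prespecified indeterminate category, and say how participants without blood are recorded.
2. Base the primary Study 1 contrasts on values below 0.40 (negative) and above 0.63 (positive). Count and report grey-zone and no-blood participants. State that these AUCs describe clear-cut biomarker cases and may be optimistic.
3. Repeat the AUCs with grey-zone participants assigned all negative and then all positive, and report the range beside the primary estimate. This answers the fair complaint that item 2 itself excludes the middle range.
4. Keep grey-zone participants in the continuous pTau-217 analysis (secondary objective ii) and in Study 2.
5. State in Section 11.3 whether 36/18/40 is net of grey-zone and missing blood results. If it is not, restate the group sizes and power with the assumed rate shown.

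The cost is wording, a few extra analysis runs, and a slightly less favourable stated sample and power. No new participants or procedures are needed to apply the rule.

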6.3. Initial Recruitment

The primary recruitment strategy involves the use of the PROTECT database. Participants who meet the inclusion criteria of the study will be sent both a patient accessible information sheet and the full information sheet, to consider whether they would like to participate in the CoCoA-PAD study. Potential participants who are interested in participating in the CoCoA-PAD study can consent for their information to be shared with the CoCoA-PAD PI.

Potential participants on the Join Dementia Research and Be Part of Research platforms will be sent both a patient accessible information sheet and the full information sheet to consider if they are interested in participating. Potential participants can then 'opt-in' on the online portal to allow the CoCoA-PAD researcher to contact them.

Potential participants approached through NHS clinics and community settings will be sent both a patient accessible information sheet and the full information sheet, and a QR code where they can register their interest and consent to be contacted.

6.4. Screening

Prior to the data collection session, potential participants will be contacted by a CoCoA-PAD researcher and asked to complete a screening questionnaire to ensure they meet the inclusion and exclusion criteria for the CoCoA-PAD study. The screening will take place over email, phone call, or online using MS Teams. In-person screening sessions will be completed if there are technological or social barriers which prevent other forms of communication. This

questionnaire will gather information establishing the potential participants identity and their eligibility to complete the study. If participants are recruited via JDR, BPR or community events, a short screening questionnaire (the Subjective Cognitive Decline Questionnaire (SCD-Q9)) and brief cognitive screening assessment (Telephone Montreal Cognitive Assessment (T-MoCA)) will be administered to determine participants eligibility and diagnostic group.

Potential participants who are eligible to participate in the CoCoA-PAD study will be provided with study related information. For participants with mild cognitive impairment (based on screening data), they will undergo a mental capacity assessment, to ensure they are making a capacitous decision to participate (see Mental Capacity Assessment Protocol). Participants who are eligible to participate and who make a capacitous decision to do so, will be invited to attend an in-person research appointment

6.5. Informed Consent

All research appointments at the Plymouth site will take place at the Brain Research and Imaging Centre (BRIC). Data collection at the Devon and North East London sites will be conducted by local NHS research teams in NHS clinical settings. The environment will be quiet and distraction free. At the beginning of the session the investigator will read through the relevant information sheet with the participant and answer any questions. For participants with a mild cognitive impairment, a mental capacity assessment will be completed again. For participants who demonstrate mental capacity to participate, and who indicate their willingness to do so, they will be asked to review the electronic consent form (see Electronic Consent Form).

Informed consent will be documented using the REDCap secure electronic data capture system, hosted on University of Plymouth servers. The consent form will display version and date control, and the wording is identical to the Electronic Consent Form attachment. Participants will be required to tick each statement. An electronic signature will be collected using a finger or stylus signature and stored securely in the REDCap database. An audit trail will record the date and time and identity of the consenting individual. The process allows participants to ask questions before completing consent, ensuring compliance with the Joint statement on seeking consent by electronic methods ([hra-mhra-econsent-statement-sept-18.pdf](https://www.hra-nhs.uk/consult/ia/pdfs/hra-mhra-econsent-statement-sept-18.pdf))

At the point of consent, participants will be asked whether they wish their General Practitioner (GP) to be informed of their participation in this research. This is optional and will not affect eligibility or clinical care. Where a participant provides explicit consent, a brief notification letter will be emailed to their GP at the time of consent, confirming study participation and outlining that the research is observational, does not alter routine care, and that no clinical results will be returned. No notification will be sent without the participant's explicit consent.

6.6. Data Collection

Participation at the Plymouth site includes the completion of demographic and health screening questionnaires (10 minutes), a 2-hour cognitive assessment, which includes a 10-minute break, a blood test by a trained NHS research nurse or phlebotomist (5 minutes), and an MRI scan (30

minutes). In total, the appointment is estimated to last approximately 2 hours 45 minutes. Participation at the Devon and North East London sites will be similar, but without the MRI scan, and therefore it will take approximately 2 hours 15 minutes. The assessment will follow the flow outlined below. However, on occasion when the MRI scan is unavailable immediately after the appointment, or if the participant indicates they are too fatigued, the participant may be asked to return for a separate appointment to complete the MRI imaging.

- Review Information Sheet
- Sign Consent Form
- Collect Demographic Information (age, gender, education etc)
- Collect Health History Information (e.g., comorbidity, sensory difficulties)
- Screening Health Questionnaires: PHQ-2, GAD-2, ISI and NRS
- Disease Severity Screening: SCD-Q9 and M-ACE
- Sensory screening (hearing, visual acuity and visual contrast sensitivity)
- CoCoA-PAD Assessment (Gorilla EB2 and MATLAB)
- Blood Test
- MRI Scan (only for participants at the Plymouth site)
- De-brief

This is a long appointment, and it may pose barriers for some participants' engagement due to fatigue, stress or medical issues. Firstly, all participants will receive breaks after every 40 minutes of research activity. Breaks are scheduled for a minimum of five minutes, with longer breaks supported, if needed. Participants will be informed in the consenting process that they can request additional breaks, also. Given that some participants may minimise discomfort, fatigue or distress, the assessor will routinely ask participants whether they are experiencing signs of fatigue, headache, brain fog, and pain. If the participant discloses this, the assessor will offer an additional break and use their clinical judgement on whether continuing the appointment is appropriate.

For participants who are unable to complete the assessment in a single appointment, they can request that the appointment is delivered over two sessions instead. These appointments would be scheduled approximately 1 week apart.

